11.4 Discontinuation of the study

Novartis reserves the right to discontinue this study under the conditions specified in the clinical study agreement.

[figure not shown]
11.5 Publication of study protocol and results

Novartis assures that the key design elements of this protocol will be posted in a publicly accessible database such as clinicaltrials.gov. In addition, upon study completion and finalization of the study report the results of this study will be either submitted for publication and/or posted in a publicly accessible database of clinical study results.

11.6 Study documentation, record keeping and retention of documents

Each participating site will maintain appropriate medical and research records for this trial, in compliance with Section 4.9 of the ICH E6 GCP, and regulatory and institutional requirements for the protection of confidentiality of subjects. As part of participating in a Novartis-sponsored study, each site will permit authorized representatives of the sponsor(s) and regulatory agencies to examine (and when required by applicable law, to copy) clinical records for the purposes of quality assurance reviews, audits and evaluation of the study safety and progress.

Source data are all information, original records of clinical findings, observations, or other activities in a clinical trial necessary for the reconstruction and evaluation of the trial. Examples of these original documents and data records include, but are not limited to, hospital records, clinical and office charts, laboratory notes, memoranda, subjects' diaries or evaluation checklists, pharmacy dispensing records, recorded data from automated instruments, copies or transcriptions certified after verification as being accurate and complete, microfiches, photographic negatives, microfilm or magnetic media, x-rays, and subject files and records kept at the pharmacy, at the laboratories, and medico-technical departments involved in the clinical trial.

Data collection is the responsibility of the clinical trial staff at the site under the supervision of the site Principal Investigator. The study case report form (CRF) is the primary data collection instrument for the study. The investigator should ensure the accuracy, completeness, legibility, and timeliness of the data reported in the CRFs and all other required reports. Data reported on the CRF, that are derived from source documents, should be consistent with the source documents or the discrepancies should be explained. All data requested on the CRF must be recorded. Any missing data must be explained. Any change or correction to a paper CRF should be dated, initialed, and explained (if necessary) and should not obscure the original entry. For electronic CRFs an audit trail will be maintained by the system. The investigator should retain records of the changes and corrections to paper CRFs.

The investigator/institution should maintain the trial documents as specified in Essential Documents for the Conduct of a Clinical Trial (ICH E6 Section 8) and as required by applicable regulations and/or guidelines. The investigator/institution should take measures to prevent accidental or premature destruction of these documents.

Essential documents (written and electronic) should be retained for a period of not less than fifteen (15) years from the completion of the Clinical Trial unless Sponsor provides written permission to dispose of them or, requires their retention for an additional period of time because of applicable laws, regulations and/or guidelines.

11.7 Confidentiality of study documents and patient records

[figure not shown]
The investigator must ensure anonymity of the patients; patients must not be identified by names in any documents submitted to Novartis. Signed informed consent forms and patient enrollment log must be kept strictly confidential to enable patient identification at the site.

11.8 Audits and inspections

Source data/documents must be available to inspections by Novartis or designee or Health Authorities.

11.9 Financial disclosures

Financial disclosures should be provided by study personnel who are directly involved in the treatment or evaluation of patients at the site, prior to study start.

12 Protocol adherence

Investigators ascertain they will apply due diligence to avoid protocol deviations. Under no circumstances should the investigator contact Novartis or its agents, if any, monitoring the study to request approval of a protocol deviation, as no authorized deviations are permitted. If the investigator feels a protocol deviation would improve the conduct of the study this must be considered a protocol amendment, and unless such an amendment is agreed upon by Novartis and approved by the IRB/IEC/REB it cannot be implemented. All significant protocol deviations will be recorded and reported in the CSR.

14.1 Concomitant medication

In general, medications listed in [Table 14-1](#) should be avoided and medications listed in [Table 14-2](#) and [Table 14-3](#) are to be used with caution when co-administered with panobinostat. The use of any of the drugs in [Table 14-1](#), [Table 14-2](#) and [Table 14-3](#) in combination with panobinostat must be discussed with the Sponsor.

14.1.1 Medications which are known to prolong the QT interval and/or induce Torsades de pointes ventricular arrhythmia should be avoided

It is of great importance to avoid such drugs listed below in [Table 14-1](#) in combination with panobinostat, especially in the presence of electrolyte abnormalities, notably decreased potassium or magnesium levels commonly associated with diuretic usage.

This is not a comprehensive list of medications which may prolong the QT interval and/or induce Torsades de pointes. This list of medications was developed in collaboration with an external cardiology consultant and represents those medications which are deemed to have an unacceptable risk of co-administration with panobinostat.

The following website may be referenced as a supplemental guide for drugs which have been associated with Torsades de pointes or prolonging the QT interval but at this time lack substantial evidence for causing Torsades de pointes: azcert.org/medical-pros/drug-lists/drug-lists.cfm.(version 3/25/2008).

Medications listed on the website which do not appear in [Table 14-1](#) above may be used with caution at the discretion of the investigator.

Ondansetron (a known CYP2D6 substrate, see [Table 14-3](#)) has prolongation but has not been shown to cause Torsades de pointes. Therefore, ondansetron is not per se prohibited when combined with panobinostat but caution is to be exercised and close monitoring for signs and symptoms of QT prolongation is recommended.

Table 14-1 Medications which are known to prolong the QT interval and/or induce Torsades de Pointes to be avoided

All Class IA antiarrhythmics	Quinidine Procainamide Disopyramide any other class IA antiarrhythmic drug
All Class III antiarrhythmics	Amiodarone Sotalol Dofetilide Ibutilide any other class III antiarrhythmic drug
Macrolide antibiotics*	Erythromycin clarithromycin
Quinolone antibiotics*	Sparfloxacin
Antifungals	pentamidine

Antimalarials	Halofantrine chloroquine
Antihistamines	Astemizole terfenadine
Anti-emetics	Chlorpromazine Domperidone Droperidol dolasetron (intravenous and oral)^
Antipsychotics	Thioridazine Mesoridazine Chlorpromazine pimozide
Miscellaneous drugs	arsenic trioxide bepriidil domperidone cisapride levomethadyl methadone
* Note: azithromycin, ciprofloxacin, levofloxacin, pefloxacin, ofloxacin, tosufloxacin, difloxacin, temafloxacin, fleroxacin, acrosoxacin, nalidixic acid and enoxacin are allowed.	
^ Intravenous dolasetron is contraindicated for preventing nausea and vomiting associated with chemotherapy based on FDA drug safety communication dated December 17, 2010. Based on this finding, both intravenous and oral dolasetron are prohibited to be taken with panobinostat.	

14.1.2 Medications which are known strong CYP3A4/5 inhibitors to be avoided

Panobinostat is a substrate of CYP3A4/5 with minor involvement of CYP2D6, and CYP2C19 in *in vitro* evaluation of its metabolism. Thus, a clinical drug-drug interaction study was conducted using ketoconazole, a strong CYP3A inhibitor, in combination with panobinostat in study CLBH589B2110.

Multiple ketoconazole doses at 400 mg increased C_{max} and AUC of panobinostat by 1.6- and 1.8-fold, respectively, but with no change in T_{max} or half-lives in 14 cancers patients. The less than 2-fold increase in panobinostat AUC upon co-administration of a strong CYP3A inhibitor is considered a weak drug inhibition and not clinically relevant, as panobinostat doses at least 2-fold greater than the evaluated 20 mg dose (i.e., 40 mg and 60 mg have been safely administered in patients. Thus, co-administration of panobinostat with a moderate or weak CYP3A inhibitor is allowed. However, clinical monitoring of signs and symptoms of panobinostat treatment related to adverse events is recommended when long-term (≥ 1 week) concomitant administration of any strong CYP3A inhibitors and panobinostat is medically indicated or investigated in a clinical study.

Patients with impaired liver function (as defined by NCI CTEP criteria) ([Synold et al 2007](#)) are recommended not to receive panobinostat concomitantly with strong CYP3A inhibitors because potential interaction has not been established in this population.

[figure not shown]

Table 14-2 Medications which are known strong CYP3A4/5 inhibitors to be used with caution

Macrolide antibiotics*	Telithromycin troleandomycin
Antifungals (azoles)	Ketoconazole Itraconazole Posaconazole voriconazole
Antidepressants	nefazodone
HIV protease inhibitors:	Indinavir Nelfinavir Ritonavir Saquinavir lopinavir
Miscellaneous drugs or products	¹ Star fruit and pomegranate product and juice convaptan

* azithromycin and regular orange juice are allowed.

¹ [Hidaka et al \(2004\)](#).

Although clarithromycin is a known strong CYP3A inhibitor, it is also known to prolong QT intervals which is listed in [Table 14-1](#) and is prohibited to be taken with panobinostat. This drug is thus not listed again in [Table 14-3](#).

This is not a comprehensive list of medications which may inhibit CYP3A4/5. The above list was compiled by using information listed under “draft guidance for industry, drug interaction studies, CDER 2006”, Indiana University School of Medicine drug interaction tables at medicine.iupui.edu/clinpharm/DDIs/ClinicalTable.asp and “drug interaction database” from University of Washington.

[figure not shown]
Additional updated versions with moderate and weak CYP3A inhibitors, which are meant to be used as a guide, may be found at the following website: medicine.iupui.edu/clinpharm/DDIs/ClinicalTable.asp.

14.1.3 Medications which are known CYP2D6 substrates to be used with caution

Panobinostat was also shown to be a CYP2D6 inhibitor (K_i 0.17 μ M) *in vitro*. Thus, clinical drug-drug interaction study with panobinostat as CYP2D6 inhibitor and dextromethorphan as CYP2D6 substrate was recently conducted in study [[CLBH589B2109](#)].

Multiple panobinostat doses increased C_{max} and AUC of dextromethorphan by a mean of 1.8- and 1.6-fold respectively, but with no change in T_{max} in 17 cancer patients. An approximately 2-fold increase in dextromethorphan AUC upon co-administration with panobinostat indicated that *in vivo* CYP2D6 inhibition of panobinostat is weak.

As the study was conducted using a sensitive CYP2D6 substrate which resulted in a weak inhibition, drugs with a large therapeutic index such as anti-emetics, anti-hypertensives, and anti-depressants are generally safe to be co-administered with panobinostat.

Patients should be carefully monitored for potential signs and symptoms of toxicity and may require dose titration or dose reduction of a sensitive CYP2D6 substrate which also have a narrow therapeutic window (e.g., the ratio of toxicity exposure is \leq 2-fold higher than the efficacious or therapeutic exposure).

Table 14-3 Medications which are known CYP2D6 substrates to be used with caution

Beta blockers	S-metoprolol Propafenone timolol
Antipsychotics	Aripiprazole Haloperidol Risperidone thioridazine
Antidepressants	Amitriptyline Clomipramine Desipramine Imipramine Fluoxetine Paroxetine Venlafaxine duloxetine
Antiarrhythmics	Mexiletine flecainide
Others	Codeine Dextromethorphan Tamoxifen tramadol
Anti-emetics	ondansetron [^]
[^] Intravenous dolasetron is a CYP2D6 substrate and contraindicated for preventing nausea and vomiting associated with chemotherapy based on FDA drug safety communication dated December 17, 2010. Please see Table 14-1 .	

This is not a comprehensive list of CYP2D6 substrates. Additional updated versions of this list, which are meant to be used as a guide, may be found at the following website: medicine.iupui.edu/clinpharm/DDIs/ClinicalTable.asp.

1.1 Document content

This Report Analysis Plan (RAP) module describes the planned statistical analyses. A clinical study report (CSR) will be produced at the completion of the trial.

This module is structured as

- A draft of Section 9.7 of the CSR [Statistical methods planned in the protocol and determination of sample size]
- A draft of Appendix 16.1.9 (Documentation of statistical methods).

Appendix 16.1.9 text will contain details of statistical methods and issues that are too long to include in the CSR text.

It is written in future tense. It will be reviewed and updated (including conversion to past tense) for entry into the clinical study report after the statistical analysis has taken place.

1.2 References

Please refer to the following documents:

- CSR template (Full or Abbreviated Clinical Study Report)
- Master Analysis Plan for LBH589
- Guidelines for content of Statistical Appendices of the Clinical Study Report
- Clinical Study Protocol for study CLBH589B2402B
- Case Report Forms for study CLBH589B2402B

2 Objectives and endpoints

Objectives and related endpoints are described in Table 2-1 below altogether with the planned analysis of collected data.

Table 2-1 Objectives and related endpoints

Objective	Endpoint	Analysis
Primary		
To evaluate long term safety data (SAEs and AEs)	Frequency and severity of AEs/SAEs	AEs/SAEs from safety database will be reviewed and reported as part of the regular pharmacovigilance activities.
Key secondary		
To evaluate clinical benefit as assessed by the investigator	Proportion of patients with clinical benefit as assessed by the investigator at scheduled visits	Proportion of patients with clinical benefit as assessed by the investigator will be summarized at scheduled visits.

3 Study design

3.1 Description of study design

This is a multi-center, open-label study to better characterize the long term safety of s.a. oral panobinostat in patients being treated in a current Novartis-sponsored, Oncology OGD&GMA study and who are benefiting from the treatment with s.a. oral panobinostat as determined by the guidelines of the parent protocol (for which the study objectives have been met) and based on the investigator's clinical judgment.

This roll-over study will not include screening period as patients will transfer directly from the parent study and commence with panobinostat as soon as they are consented and meet inclusion criteria of the roll-over protocol. All patients must report to the study site for their first visit and commence study participation. At that time, a quarterly (12 +/- 2 weeks) supply of oral panobinostat will be dispensed to the patient or as per local practice.

Patients must return to the study center on a quarterly (every 12 +/- 2 weeks) basis for resupply of study medication at which time limited drug dispensing information will be collected. Changes in dosing which might occur any time during the study treatment will be documented on the dose administration page.

Patients may return to the study center more frequently at the physicians' discretion as clinically indicated or as per standard of care, however, data from these visits will not be captured in the eCRF, but rather only in the source documents at the study center.

Reported AEs/SAEs, defined as per standard Novartis guidelines, will be collected continuously throughout the study in the safety database.

Patients entering the roll-over protocol should be followed at the investigator's discretion for known and/or clinically notable AEs that occur on panobinostat treatment as described in the current version of the [Investigator Brochure].

[figure not shown]
Patients will continue to be treated in the roll-over protocol until they are no longer benefiting from the s.a. oral panobinostat treatment, develop unacceptable toxicities, withdraw consent,

are non-compliant to the protocol, the investigator feels it is no longer in the patient's best interest to continue s.a. oral panobinostat therapy, pregnancy occurs or the patient dies, whichever comes first.

A patient will reach the end of the study treatment when s.a. oral panobinostat treatment is permanently discontinued. A 30-day safety follow-up after last dose of study drug should be conducted.

The study is expected to remain open for 5 years or until such time that enrolled patients no longer need treatment with panobinostat, whichever occurs earlier.

Figure 3-1 Basic Study Design

*Note: The starting dose and schedule of s.a. panobinostat will be the same as the last assigned dose and schedule received in the parent study.

3.2 Timing of interim analyses and design adaptations

No interim analyses are planned.

3.3 Definition of end of the study

End of study is defined as either a 5 year duration or when all patients in this study have permanently discontinued panobinostat treatment and the end of treatment visit plus the 30-day safety follow up have been performed for each patient (and no further follow-up is needed), whichever comes earlier.

3.4 Early study termination

The study can be terminated at any time for any reason by Novartis. Should this be necessary, the patient should be seen as soon as possible and the same assessments should be performed as described in [Section 7.1.3 of the study protocol]. The investigator may be informed of additional procedures to be followed in order to ensure that adequate consideration is given to the protection of the patient's interests. The investigator will be responsible for informing IRBs and/or ECs of the early termination of the trial.

4 Population

4.1 Patient population

The study population is constituted of patients with various malignancies who participated in a Novartis-sponsored, Oncology OGD&GMA clinical trial for their specific indication and qualify to transfer to this roll-over protocol.

The investigator or designee must ensure that only patients who meet all the following inclusion and none of the exclusion criteria are offered treatment in the study.

5 CSR Section 9.7 – Statistical methods planned in the protocol and determination of sample size

5.1 CSR Section 9.7.1 – Statistical and analytical plans

The statistical analysis of this study will be performed by Novartis personnel. SAS[®] version 9.3 or later version will be used in all analyses.

This study follows an open-label, multi-center design. It is planned that the data from all centers that participate in this protocol will be pooled and utilized.

5.2 Data included in the analysis

Patients will continue to be treated in the roll-over protocol until they are no longer benefiting from the s.a. oral panobinostat treatment, develop unacceptable toxicities, withdraw consent, are non-compliant to the protocol, the investigator feels it is no longer in the patient's best interest to continue s.a. oral panobinostat therapy, pregnancy occurs or the patient dies, whichever comes first.

A patient will reach the end of the study treatment when s.a. oral panobinostat treatment is permanently discontinued. A 30-day safety follow-up after last dose of study drug should be conducted.

The study is expected to remain open for 5 years or until such time that enrolled patients no longer need treatment with panobinostat, whichever occurs earlier.

All data reported in the database will be included in the analyses.

5.3 Analysis populations

The following populations will be considered in the data analysis:

Full Analysis Set (FAS): consists of all patients who received at least one dose of panobinostat after enrolling into the roll-over protocol.

Safety set: consists of all patients who received at least one dose of panobinostat after enrolling into the roll-over protocol.

FAS and safety set are defined the same.

5.4 Patients and treatments

5.4.1 Patient disposition

Patient disposition will be summarized for the FAS by the number of patients who discontinue along with the reason for discontinuation according to the data recorded on the end of treatment CRF panel.

5.4.2 Background and demographic characteristics

Age and gender will be summarized. Patients' parent studies will also be summarized so patients in this study can be linked to their parent studies for more information.

5.4.3 Extent of study drug exposure

5.4.3.1 Drug exposure

All study medication data will be summarized using the safety set.

Duration of exposure will be summarized by dose regimen. For the purposes of analysis, the following rules will be applied:

If the last entry in the dose administration CRF page has a reported end date which is non-missing and before the last known date patient took the study drug from the end of treatment CRF page, the gap between those 2 dates will be filled-in by imputing the dose assigned at the beginning of the study.

This rule will be applied before using any of the following definitions.

Date of first dose is defined as the date of first intake of panobinostat in this study. This will be considered as treatment day 1. There is no study day 0.

Date of last dose is defined as follows:

• For patients who discontinued study treatment, the date of last dose is defined as the date of the last non-zero dose of panobinostat reported in the dose administration CRF page.

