6.1.4 Guidelines for continuation of treatment

The starting dose of oral panobinostat should be the same as the last assigned dose and schedule that was given in the parent study. Assigned dose is the dose as designated by investigator and does not include unintended changes or error in dosing in parent protocol.

Dose modification thereafter (following the starting dose) may be done at the discretion of the investigator based upon what is in the patient's best interest.

In case patients do not tolerate the dosing schedule, dose adjustments are permitted in order to keep the patient on study drug. These dose adjustments may be delays in dosing and/or reductions in the dose being administered. Dosing should always be temporarily discontinued if the physician determines it is in the best interest of the patient. All dose modifications should be recorded in the source documents and on the Dosage Administration Record Form.

Patients receiving a reduced dose of panobinostat due to toxicity who are clearly benefiting from panobinostat and whose AE(s) remain grade $<$ or $=$ 1, which the patient believes is/are tolerable may at the discretion of the Investigator after agreement by the Sponsor return to the initial dosage in 5mg/increments. Dose re-escalation should be reviewed on a case basis and requires agreement between Sponsor and Investigator. No more than 2 dose reductions are permitted (i.e. the minimum dose patients may receive is 5 mg/day).

[figure not shown]

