6.2.1 Non-Cardiac Toxicity Dose Modifications

Treatment dose and/or schedule modification may be required based on individual tolerability. Clinical judgment on how to continue the treatment should be exercised when a patient experiences adverse drug reactions.

If a dose reduction is required, the dose of panobinostat should be reduced by decrements of 5 mg (i.e. from 20 to 15 mg or from 15 to 10 mg). The dose should not be reduced below 10 mg daily and the same treatment schedule should be maintained.

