2.9 Study drug exposure

Duration of study treatment exposure [months] will be summarized by dose regimen of panobinostat. In addition, the duration of exposure to study treatment will be categorized into time intervals in months; frequency counts and percentages will be presented for the number of patients in each interval. The safety set will be used for all summaries and listings.

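### SAP 5.4.3.1 fills an end-of-treatment gap in the dosing records with the starting dose, which contradicts the latest record for a patient still on a reduced dose

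*SAP*

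**What the plan says.** SAP 5.4.3.1 (Drug exposure) sets a gap rule for the dosing data. The trigger is: "If the last entry in the dose administration CRF page has a reported end date which is non-missing and before the last known date" of intake shown on the end-of-treatment page. In that case "the gap between those 2 dates will be filled-in by imputing the dose assigned at the beginning of the study". The SAP adds: "This rule will be applied before using any of the following definitions". There is no exception for a patient whose dose changed during the study, and no other section overrides the rule.

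The filled data feed the exposure summary. SAP 5.4.3.1 states: "Duration of exposure will be summarized by dose regimen". Appendix 16.1.9, section 2.9, repeats this: "Duration of study treatment exposure [months] will be summarized by dose regimen of panobinostat". Section 2.9 also plans counts and percentages of patients by duration interval. *Dose regimen* is not defined.

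The protocol expects doses to change. Section 6.1.4 says: "Dose modification thereafter (following the starting dose) may be done at the discretion of the investigator", and, for patients who do not tolerate the schedule, "These dose adjustments may be delays in dosing and/or reductions in the dose being administered". Section 6.2.1 gives the step size: "the dose of panobinostat should be reduced by decrements of 5 mg". Protocol 4.1 and 6.5 and SAP 3.1 have dose changes recorded on the dose administration page.

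**The concern.** The gap lies at the end of treatment, the point furthest from the starting dose. When the rule is applied, a later dose is normally already on the dose administration page, so the rule passes over the nearest record in favour of the most distant one.

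For a patient who was reduced and has not returned to the starting dose, the imputed interval contradicts the latest record. It also creates a dose history that does not follow the protocol's own path. Section 6.1.4 makes re-escalation subject to sponsor agreement and takes it in 5 mg steps, whereas a patient reduced from 20 mg to 10 mg would appear to go straight back to 20 mg.

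What is at stake is how exposure time is split between dose levels. In a study of long-term safety, time wrongly credited to the starting dose makes that dose look longer tolerated than the records show. The patients affected are those whose dose was reduced.

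**Working it through.** The documents state no exposure figure, so there is nothing to reproduce. The check is by cases and then by day counts.

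**Cases, by the last record before the gap**

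- *Dose never changed.* The starting dose and the last recorded dose agree, so the rule does no harm.
- *Reduced, then returned to the starting dose* (possible under Protocol 6.1.4). They agree again.
- *Still on a reduced dose.* The rule inserts a dose that the last record contradicts.
- *Held (zero dose).* The end-of-treatment page shows that drug was taken later. Protocol Tables 6-3 and 6-4 allow some patients to resume at the same dose and others at a reduced dose, so the starting dose may or may not be right.

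**Day counts for the reduced-dose case**

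These inputs are assumptions: a = 84 days at 20 mg, b = 84 recorded days at a reduced dose, and a gap of g days. The visit interval of 12 ± 2 weeks (70 to 98 days, Protocol 7.1.3) serves only as a scale for g. Nothing says a gap lasts that long, so shorter gaps are shown too.

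Total T = a + b + g. Share of time at 20 mg under the SAP rule = (a + g)/T. Share if the last recorded dose is carried into the gap = a/T.

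| Gap g (days) | T (days) | Days at 20 mg, SAP rule | Share | Days at 20 mg, last recorded dose | Share |
|---|---|---|---|---|---|
| 7 | 175 | 91 | 52.0% | 84 | 48.0% |
| 28 | 196 | 112 | 57.1% | 84 | 42.9% |
| 70 | 238 | 154 | 64.7% | 84 | 35.3% |
| 84 | 252 | 168 | 66.7% | 84 | 33.3% |
| 98 | 266 | 182 | 68.4% | 84 | 31.6% |

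T is the same under both rules. For g = 84 it is 252/30.4375 = 8.28 months, using the SAP's month length. Nine patients had been enrolled at Amendment 01, so one affected patient would be 1/9 = 11.1% of the set.

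**Last-dose date and adverse event window**

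SAP 5.4.3.1 takes the last-dose date as the last non-zero dose on the dose page, after the gap rule. Any non-zero imputed dose therefore gives the same date and the same 30-day window. A zero or unfilled gap does not. With an assumed 84 days on drug, a 28-day hold and a 28-day gap:

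- Non-zero dose imputed: last dose on day 84 + 28 + 28 = 140, and the window ends on day 140 + 30 = 170.
- Zero carried forward, or gap left unfilled: last dose on day 84, and the window ends on day 84 + 30 = 114.

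A replacement rule must therefore specify a non-zero dose. Appendix 16.1.9, section 2.1.2, takes the last-dose date from the end-of-treatment page instead. That difference in source also needs reconciling, but it is separate from the question of which dose to impute.

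**The case against.** The strongest reply is that no planned result may change. The protocol treats dose and regimen as separate items (2.3, 6.1.1) and in places uses regimen to mean schedule (1.2.1.2). Section 6.2.1 keeps the schedule the same when the dose is reduced. Appendix 16.1.9, section 2.9.1, gives one duration per patient, interruptions included, with no formula for dividing it by dose level. If regimen means schedule, or each patient is assigned a single regimen, the imputed dose leaves the duration summaries essentially unchanged. This stands as a condition on the effect. It does not justify the rule, because the SAP leaves the term open and Protocol 6.2.1 also allows schedule changes.

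Second, gaps may be rare and short. Dose changes are to be recorded whenever they occur, and Protocol 9.3 and 9.4 provide validation checks and queries before database lock. That is fair. The rule is a fallback, and the documents give no frequency or length.

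Third, SAP 5.4.3.2 lists all dosing records, with reasons for changes, so readers can see the recorded doses. This limits the harm, although the summary could then disagree with the listing.

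A reader might go further and infer that the rule doubles the drug credited to a patient reduced from 20 mg to 10 mg (20/10 = 2). The nominal dose within the gap does double, but the SAP plans no cumulative dose or dose intensity, so that ratio enters no planned output. A reader might also infer that every patient whose dose was changed or held is misclassified. The re-escalated and held cases show otherwise.

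**Conclusion.** The point holds, at minor severity. For a patient still on a reduced dose at the last record, the rule imputes a dose that the record contradicts, when a better value is already on the same page. If *dose regimen* distinguishes dose levels, every gap day moves from the reduced dose to the starting dose. In the assumed case, the share of time at the starting dose rises from 48.0% to 52.0% for a 7-day gap and from 31.6% to 68.4% for a 98-day gap. These sizes rest on assumed gap lengths and an assumed dosing history.

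A reader might infer that the primary safety tables are biased. The documents do not support that. Adverse events are counted within a time window and are not broken down by dose level (Protocol 10.5.3.2, SAP 5.6). The window, the last-dose date and total duration are the same for any non-zero imputed dose. The duration-interval counts in Appendix 16.1.9, section 2.9, are likewise unaffected.

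**What to change.** In SAP 5.4.3.1, replace the starting dose as the imputed value with the last non-zero dose and regimen recorded on the dose administration page before the gap.

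If the last record is a zero dose, query the site. If the query is unresolved at database lock, impute the last non-zero dose, so that the last-dose date and the on-treatment window are kept. Flag all imputed intervals in the dose listing.

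It would help to state in the same place whether *dose regimen* means dose level, schedule or both, since the effect of the rule depends on it.

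The cost is a short SAP edit, a small programming change and perhaps a few site queries. Time shown at the starting dose may become slightly shorter.
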